**1. Hypothesis:**

Intra articular injections with autologous platelet rich plasma (PRP) will improve symptoms, recovery time, and imaging appearance using delayed gadolinium enhanced MRI of cartilage (dGEMRIC) or Non-contrast MRI in patients suffering from stable juvenile osteochondritis dissecans of the knee when compared with conservative therapy.

**2. Specific Aims:**

In adolescents with osteochondritis dissecans of the knee:

**Aim 1.** Compared to conservative therapy alone, determine whether intra-articular platelet injections combined with conservative therapy lead to greater cartilage healing.

**Efficacy Endpoint** – Measurement by glycosaminoglycan (GAG) content (T1GD) on dGEMRIC, or by healing changes of MRI diagnostic cartilage sequences, using the DiPaola classification system.

**Aim 2.** Compared to conservative therapy, determine whether intra-articular platelet injections lead to improvements over time in:

**Efficacy Endpoint 2.1.** Pain, as measured by the pain subscale of the KOOS-child.

**Efficacy Endpoint 2.2.** Performance of activities of daily living, as measured by the ADL subscale of KOOS-child.

**Efficacy Endpoint 2.3.** Sport performance, as measured by the sports subscale of the KOOS-child.

**Efficacy Endpoint 2.4.** Overall function and symptom reduction, as measured by the pedi-IKDC.

**Aim 3.** Correlate dGEMRIC findings or MRI diagnostic cartilage sequence findings on imaging studies with measures of functional recovery and symptom reduction.

**Protocol #: 13-2797**

**Efficacy Endpoint** – statistical evaluation of outcomes between the two patient populations

### **3. Background:**

#### **a. Osteochondritis dissecans:**

Osteochondritis dissecans (OCD) is an osteochondrosis characterized by osseous necrosis followed by reossification and healing. There are both juvenile and adult forms of this condition. The most common anatomic location for this to occur is the knee, with the most frequent involvement being the medial femoral condyle. This can also occur in the elbow, ankle, or hip. The etiology is unknown though repetitive micro trauma and or ischemia are postulated as possible inciting factors. MRI is frequently used in the diagnosis of osteochondral lesions associated with OCD. Lesions can be stable or unstable. Stable lesions in patients with open physis, juvenile form, are typically treated conservatively, while unstable lesions traditionally require surgical intervention. The adult form is similar, though the patient's physis are fused. This process affects adolescent males three times more than females.

#### **b. Autologous platelet-rich plasma (PRP):**

The therapeutic use of autologous platelet-rich plasma (PRP) constitutes a relatively new biotechnology that has been a breakthrough in the stimulation and acceleration of soft-tissue, bone and cartilage healing [1-3]. The application of PRP has been extended to many different fields, including orthopedics, sports medicine, dentistry, cosmetic and periodontal medicine, plastic, and maxillofacial surgery [4]. The efficiency of this process lies in the local and continuous delivery of a wide range of growth factors and proteins, mimicking the needs of the physiological wound healing and reparative tissue processes [4].

In this process a preparation rich in growth factors (PRGF) combines the advantage of an autologous fibrin clot that will aid in hemostasis as well as provide growth factors in high concentrations to the site of a tissue defect. The platelet-rich plasma preparation encourages the release and slow delivery of growth factors from harvested platelets, activated by endogenous thrombin, and is used as a biological enhancer in the healing of fractures, lumbar fusions, cartilage defects, muscle tears, and tendon lesions, thus promoting initiation and early maturation of bone and soft tissue formation [1, 2, 4-7] which involves a more physiologic repair with less scar tissue[7].

Growth factors offer promising treatments for enhanced regeneration of cartilage in focal articular cartilage defects or in situations of more widespread cartilage loss such as those that occur in osteoarthritis (OA). Numerous anabolic growth factors stimulate chondrocytes synthesis of proteoglycans, aggrecan, type II collagen, induce synoviocyte and mesenchymal stem cell (MSC) proliferation, drive chondrogenic differentiation of MSCs, and decrease the catabolic effects of cytokines such as interleukin-1 (IL-1) and the matrix metalloproteinases (MMP) [3].

The source of the new PRP preparation consists of a limited volume of plasma enriched in platelets, which is obtained from the patient. Once the platelet concentrate is activated a myriad of growth factors and proteins are released, progressively, into the local environment, contributing to the accelerated postoperative wound healing, tissue repair, and vascularization [3, 8].

The application of PRP in cartilage repair is relatively new and therefore limited publications are available investigating its use. Chondrocytes and MSCs exposed to PRP both have increased cell proliferation and cartilage extracellular matrix synthesis of proteoglycans and collagen type II compared with controls [9]. Synoviocytes from patients with OA cultured in PRP demonstrated increased hyaluronic acid production and secretion, suggesting that PRP could potentially serve as an endogenous source of chondroprotection and joint lubrication after intra-articular application [10]. In a rabbit model, osteochondral defects were treated with either autogenous PRP in a poly-lacticglycolic acid (PLGA) carrier, PLGA alone, or left untreated [11]. The PRP group demonstrated a higher extent of cartilage regeneration as well as an increased production of the glycosaminoglycans in the ECM.

In a cohort of 30 patients comparing injections of PRP with hyaluronic acid (HA) in the management of OA, the success rate for the pain subscale reached 33.3% for the PRP group compared with 10% for the HA group ( $p = 0.004$ )[12]. Additionally, the percent reductions in the physical function subscale and overall WOMAC at 5 weeks were also associated solely with treatment modality in favor of PRP with  $p = 0.043$  and  $p = 0.010$ , respectively.

Kon et al. treated 115 knees of patients with four intra-articular PRP injections given every 21 days and followed the patients for 12 months [8]. Patients evaluated in this study included 58 with degenerative chondral lesions (Kellgren-Lawrence 0), 33 with early OA (Kellgren- Lawrence I-III), and 24 with advanced OA (Kellgren- Lawrence IV). A substantial improvement in International Knee Documentation Committee (IKDC) and EuroQol (EQ-VAS) scores was noted at the end of therapy and at both the 6- and 12-month time points. The IKDC subjective scores as well as the EQ-VAS scores also demonstrated major improvements at the end of therapy. The authors concluded that treatment with PRP is safe and effective at improving pain, function, and quality of life in patients with degenerative articular pathology.

A separate study by our sub-investigator, [name] showed that osteochondral lesions of the ankle treated with intra-articular injections of PRP and HA resulted in a decrease in pain scores and an increase in function for at least 6 months, with minimal adverse events. Platelet-rich plasma treatment led to a significantly better outcome than HA.[9]

Recently, a randomized control trial (RCT) evaluating the effect of PRP on early osteoarthritis of the knee showed significant clinical improvement at both 6 months and 1 year. Platelet-rich plasma seemed to result in no change by MRI per knee compartment in at least 73% of cases at 1 year. No adverse effect was reported with the use of PRP [13].

### **c. dGEMRIC (delayed gadolinium-enhanced MRI of cartilage)**

Intravenous injection of gadolinium allows for rapid penetration of contrast agent into the articular cartilage due to penetration both from the synovial fluid as well as the subchondral bone. The patient needs to move the joint after injection and the dGEMRIC imaging needs to occur within a 30–100 minute time window after injection for a reliable biochemical assessment of the articular cartilage [14, 15].

Gadolinium based biochemical MRI in the form of dGEMRIC has been established as an important modality in the imaging of articular cartilage. [14-25]. dGEMRIC is sensitive to the glycosaminoglycan (GAG) content in the cartilage. When the negatively charged gadolinium contrast is administered, there is an uptake in hyaline cartilage in an inverse proportion to the GAG content [17]. Degenerated cartilage contains less overall quantity of GAG, therefore the concentration of gadolinium is high compared to the relatively low amount of gadolinium that accumulates in healthy cartilage. Consequently, T1 measurements performed post gadolinium injection can give an indirect reflection of GAG content of cartilage, due to the fact that gadolinium decreases the T1 relaxation time [16, 25, 26].

**d. Non-contrast MRI of the knee/lower extremity**

A non-contrast Magnetic Resonance Imaging (MRI) of the knee is a diagnostic imaging procedure which utilizes magnets to produce detailed images of the knee structure. The delivery of contrast is not required for this imaging procedure.

**e. Preliminary Studies:**

The application of PRP in cartilage repair is relatively new and therefore limited publications are available investigating its use. Recently, a randomized controlled study comparing HA versus PRP in the short term treatment for symptomatic knee osteoarthritis showed plasma rich in growth factors showed superior short-term results when compared with HA in a randomized controlled trial, with a comparable safety profile, in alleviating symptoms of mild to moderate osteoarthritis of the knee [27]. Another study evaluating the effects of PRP in osteoarthritis of the knee together with MRI reported significant clinical improvements at 12 months post injection. According to MRI results, there was no change in the appearance of osteoarthritis 1 year after platelet-rich plasma therapy in 83.3% of all cases when compared with baseline (N = 12) with lateral femoral and tibial compartment involvement. Similarly, there was no change in 73.3% of the cases with medial compartment involvement, although these values did not reach statistical significance. The appearance of medial compartment osteoarthritis improved in 1 knee (6.7%) after 1 year. This is in contrast to some longitudinal studies that suggest an annual decrease of up to 4% to 6% of cartilage volume in knee osteoarthritis compartments. [13]

Recently, Gobbi et al evaluated the effect of PRP in 50 patients with osteoarthritis. At 12 months follow up, patients had improved clinical symptoms with no adverse effects reported [28].

In a pilot study of 100 patients with osteoarthritis of the knee receiving intra-articular PRP injections, favorable results with pain reduction and improved function were reported. Patients were followed up at 2, 6, 12, and 24 months. Statistically significant improvement was observed in all the variables[29].

Our Sub-Investigator [name] et al evaluated the effect of intra-articular injections of PRP compared to HA in osteochondral lesions of the talus. Both groups significantly improved clinical symptoms. When comparing both treatments groups, PRP produced a significantly greater improvement than HA [9]. Minor discomfort and mechanical pressure were common reports at the injection site in both groups.

Battaglia et al recently reported the outcomes of injection of PRP for OA of the hip. Twenty patients, with a mean age of 52 years, who presented symptomatic OA of the hip were treated with a total of 3 intrarticular injections of PRP. Patients were prospectively evaluated at 1, 3, 6, and 12 months follow up. All patients had significantly improved clinical symptoms. No major complications or adverse events occurred at the moment of injection or in the follow-up period. Ten patients reported a slight pain during or after the injection, which spontaneously resolved in 1 or 2 days [30].

Gillis et al evaluated autologous chondrocyte transplantation in patients with full thickness chondral lesions of the knee utilizing dGEMRIC to indirectly quantify the GAG content of cartilage at the site of transplant, adjacent to the site of transplant, and distant to the site of transplant. The study demonstrated that GAG levels in grafts that had been implanted at 12 months or greater had GAG levels comparable to adjacent and remote cartilage. [31]

Typically, patients with Juvenile Osteochondritis Dessicans will heal without treatment within a 12 month period, therefore it was recently decided that the research dGEMRIC MRI would be performed 6 months from the time of the consent instead of 12 months. [32]

#### **4. Research Methods**

We propose a randomized controlled clinical trial in children (aged 10-17) with osteochondritis dissecans (OCD) comparing the use of platelet-rich plasma (PRP) therapy and conventional therapy compared to conventional therapy alone.

The goal of this research is to test the hypothesis that intra articular injections with autologous PRP will improve symptoms, recovery time, and imaging appearance using delayed gadolinium enhanced MRI of cartilage (dGEMRIC) or MRI diagnostic cartilage sequence findings in patients suffering from stable juvenile OCD of the knee when compared to conservative therapy. Specifically, we aim to determine whether intra-articular platelet injections when compared to conservative therapy over time, lead to greater cartilage healing (measured by gadolinium accumulation or measured by healing on Non-contrast MRI, utilizing the DiPaola classification system), improvement in pain, improvement in performance of activities of daily living, improvement in sport performance, and improvement in overall function and symptom reduction.

Finally, we aim to determine if dGEMRIC findings or MRI diagnostic cartilage sequence findings on imaging studies correlate with measures of functional recovery and symptom reduction.

All protocol procedures other than patient randomization, PRP injections, and the 6 month dGEMRIC or Non-Contrast MRI are considered routine standard of care procedures. These three procedures are being conducted for research purposes in this study.

#### **Description of Population to be Enrolled:**

This study aims to enroll 24 subjects, 12 patients for each of the two treatment arms, all with documented stable juvenile osteochondritis dissecans identified via imaging. We believe 24 patients could be included during the time period allotted for the study based on the number of patients suffering from OCD seen annually at the Children's Hospital Sports Medicine Clinic.

#### **Patient Recruitment**

A diagnostic knee MRI (through CHCO or an outside facility) will have been performed as standard of care prior to study participation, utilizing dGEMRIC, a Non-contrast MRI or a MRI with and without contrast in patients with a high clinical suspicion for osteochondritis dissecans. The study is posted on the clinicaltrials.gov website and patients and/or their parents may call and inquire about eligibility.

Lesions will be classified according to Di Paola et al classification [33]

This uses 5 stages as follows:

Grade 1: Small change of signal without clear margins of fragment,

Grade 2: osteochondral fragment with clear margins but without fluid between fragment and underlying bone,

Grade 3: fluid is visible partially between fragment and underlying bone,

Grade 4: fluid is completely surrounding the fragment, but the fragment is still in situ;

Grade 5: fragment is completely detached and displaced.

Only patients with Di Paola stage 1 or 2 lesions will be approached for study participation and consented into the study.

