### **Inclusion Criteria**

1. Male or female age 10 - 17 inclusive with open physis confirmed by MRI
2. Documented symptomatic stable juvenile osteochondritis dissecans of the knee based on MRI without changes of osteoarthritis and no prior history of knee surgery. The MRI diagnosis must be within a 3 month time period prior to consent.
3. The patient must be able to hold still without sedation for approximately 1 hour and must pass MRI screening evaluation for retained metal.
4. Patients with Di Paola stage 1 or 2 lesions

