### **Research MRI utilizing dGEMRIC or Non-contrast MRI**

Once the intrarticular PRP injections have been administered, a follow-up MRI will be performed utilizing dGEMRIC or Non-contrast MRI at 6 months from the initial visit. Mean T1 values on dGEMRIC will be calculated by drawing a region of interest at the site of hyaline cartilage pathology, adjacent to the site of pathology within the hyaline cartilage, and distant to the site of pathology within the hyaline cartilage on initial and follow up imaging. If the follow-up imaging is with a Non-contrast MRI, the DiPaolo classification system will be used to quantify interval change.

Knee MRI with dGEMRIC will be performed in the standard manner. Upon arriving to the radiology department for the MRI, a pregnancy test will be administered for all female participants of child bearing potential. An institutional MRI screening form will be given to each patient and parent and reviewed with the MRI technologist. If there is any retained metal (pacemaker, metallic bb, orthopedic hardware), MRI will not be performed. If there is no contradiction to MRI based on the institutional screening form, the patient will have an IV placed. Using weight based dosing, .04 ml/kg, injection of gadolinium will be administered. The patient will then be asked to exercise for 30 minutes, which will be performed by walking around the hospital. The patient will then return to the MRI suite in the department of radiology. Standard screening for retained metal will be performed prior to entering the MRI scanning area. If the parent/guardian wishes to accompany the child for the MRI scan, they will be screened in identical fashion. In the MRI scanner, the patient will be required to lie still for approximately 1 hour, the duration of the scan. The patient will have the option of watching a

movie or listening to music on ipod or similar device (plugged in outside the scanner in technologist area) during imaging. No sedation will be given. There is no ionizing radiation associated with MRI.

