### **Proposed statistical analysis for Aim 3: Correlation of MR Findings and Measures of Functional Recovery and Symptoms**

We plan to fit four general linear univariate models with 6-month T1GD as the outcome. The primary predictor for each model will be the 6 month measurements of the pain subscale of KOOS-child, the ADL subscale of the KOOS-child, the sports subscale of the KOOS-child, and the pedi-IKDC, respectively. In each model, age will be included as a covariate. We will test the null hypothesis of no association between the functional measure and T1GD findings on MR and/or no decrease in DiPaolo score, using an F test. All hypotheses will be tested at the Bonferroni corrected alpha level of  $0.05/4 = 0.0125$ .

Interim analysis and planned interim power analysis.

Because this study has never been done in children, the estimates for power analysis may be incorrect, and the effect of the treatment may be better or worse than that reported in the literature. Thus, after the first six study participants have been recruited, treated, and followed, the investigators will report blinded data to the study statistician, who will perform an interim power analysis using the methods of Gurka et al., 2007 [41].

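### The Di Paola scale as listed has no grade for a resolved lesion and entry is limited to grades 1 and 2, so healing on non-contrast MRI may be missed or scored inconsistently

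*Combined protocol and SAP*

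**What the plan says.** Patient Recruitment introduces the classification with "This uses 5 stages as follows" and lists grades 1 to 5. The two lowest are "Grade 1: Small change of signal without clear margins of fragment" and "Grade 2: osteochondral fragment with clear margins but without fluid between fragment and underlying bone". Grades 3 and 4 add fluid partly and then wholly around the fragment, and grade 5 is a detached, displaced fragment. No listed grade means normal or healed.

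Entry is limited to the two lowest grades, in Patient Recruitment ("Only patients with Di Paola stage 1 or 2 lesions will be approached for study participation and consented into the study") and again in the Inclusion Criteria ("Patients with Di Paola stage 1 or 2 lesions").

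Specific Aims allows the Aim 1 endpoint to be T1GD on dGEMRIC, "or by healing changes of MRI diagnostic cartilage sequences, using the DiPaola classification system". The section on the research MRI says how the second option is quantified: "If the follow-up imaging is with a Non-contrast MRI, the DiPaolo classification system will be used to quantify interval change". The direction of improvement appears only in the Aim 3 analysis, which refers to "no decrease in DiPaolo score". Under 6 month Research MRIs, patients whose diagnostic scan was non-contrast, or was done with and without contrast, all have non-contrast follow-up.

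The Preliminary Studies section says that these lesions usually heal untreated within a year, and gives this as the reason for moving the research MRI from 12 to 6 months.

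**The concern.** Complete resolution is the outcome the trial hopes to see more of, and the protocol itself regards it as common within a year. The scale as listed has no place to record it. For non-contrast patients this is the only Aim 1 healing measure the plan defines, and the Power Analysis section names Aim 1 as the primary endpoint.

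Two things are at stake. First, if readers put resolved lesions in the nearest listed grade, grade 1 entrants who heal look unchanged, and any benefit of PRP is diluted towards no difference. Second, if readers instead leave the field blank or write in their own category, the outcome depends on individual habit. The randomization section mentions no stratification by entry grade and the Aim 1 model adjusts only for age, so a chance imbalance in entry grade between small arms would also carry through to the comparison.

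**Working it through.** **Moves available on the listed scale**

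| Entry grade | Best recordable follow-up | Maximum improvement | Worsening recordable |
|---|---|---|---|
| 1 | 1 | 0 grades | 2 to 5 |
| 2 | 1 | 1 grade | 3 to 5 |

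This part needs no assumption. It follows from the grade list, the entry criterion and the interval-change rule.

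**Is there a plan figure to reproduce?** No. The documents give no sample size, test, significance level or expected rate for the Di Paola outcome. The stated power of 0.93 concerns T1GD and does not enter here.

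**Size, by illustration.** Inputs:

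- From the protocol: 12 patients per arm. This is an upper bound, because it supposes that every patient has non-contrast follow-up and none is lost. The Power Analysis section allows for losing up to two per arm.
- Assumed: true full-healing proportions *h*; share *g* entering at grade 1, the same in both arms; healing independent of entry grade; only full healing counts as improvement; a resolved grade 1 lesion is recorded as grade 1; a two-sided Fisher exact test at 0.05.

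Observable proportion = *h* × (1 − *g*). Observable arm difference = (*h*₁ − *h*₂) × (1 − *g*). The difference therefore shrinks by exactly the share entering at grade 1.

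Worked line for 90% versus 30% and *g* = 50%: 0.90 × 0.5 = 45% and 0.30 × 0.5 = 15%, so a true difference of 60 points appears as 30.

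Exact power, by summing the binomial probabilities of all tables with p ≤ 0.05:

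| Scenario | With a healed category | *g* = 25% | *g* = 50% | *g* = 75% |
|---|---|---|---|---|
| 90% vs 30%, 12 per arm: observable rates | 90 vs 30 | 67.5 vs 22.5 | 45 vs 15 | 22.5 vs 7.5 |
| Power | 0.83 | 0.50 | 0.22 | 0.05 |
| 60% vs 30%, 12 per arm: observable rates | 60 vs 30 | 45 vs 22.5 | 30 vs 15 | 15 vs 7.5 |
| Power | 0.21 | 0.12 | 0.05 | 0.01 |
| 90% vs 30%, 6 per arm: power | 0.27 | 0.12 | 0.03 | 0.002 |

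The six-per-arm row stands for the case where half of each arm has dGEMRIC follow-up. The documents do not give the actual split.

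**The case against.** A reader might infer that the plan scores a healed grade 1 lesion as unchanged, so that healing is certain to be undercounted. The documents do not support that. Grade 1 requires a visible signal change, so a lesion with none does not meet its definition. A reader might assign 1, call the knee normal or leave the item blank. What the documents show is an undefined score, and undercounting is the risk that follows from it. This objection stands.

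Several others also stand:

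- Worsening remains recordable, so a treatment difference through less progression could still be seen, even among grade 1 entrants.
- Partial improvement from 2 to 1 is recordable. The illustration ignores it and so understates what the scale can show.
- The 90% versus 30% rates are assumed, and they happen to give good starting power. At 60% versus 30% the outcome is weak with or without the change.
- The plan specifies no Aim 1 test for Di Paola grade, so no planned power is being lost, and the 0.93 for T1GD is not called into question.
- How many lesions would show no residual signal by 6 months is unknown. The protocol's statement about healing refers to 12 months.

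None of this removes the core point: the listed scale has nothing below grade 1, and no rule says what to record when the lesion is gone.

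**Conclusion.** The concern holds as a gap in the measurement scale. For the non-contrast patients, grade 1 entrants cannot be recorded as improved on the listed grades. Full and partial healing of a grade 2 lesion cannot be told apart, and a resolved lesion has no defined score.

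The size cannot be fixed from the documents, because neither the entry-grade mix nor the number with non-contrast follow-up is given. If healing does not depend on entry grade, only full healing counts and resolved grade 1 lesions are recorded as grade 1, the observable arm difference falls by the share entering at grade 1. The power figures only illustrate that relation under assumed rates and a test the plan does not name. They do not estimate this trial's power. T1GD is continuous and is untouched. This is a cheap improvement, not a flaw that invalidates the trial.

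**What to change.** Add one follow-up category below grade 1, no residual signal change, to the blinded reading form, with a line telling readers to use it when the lesion is no longer visible. Analyse the 6-month grade including that category, or improved yes/no, adjusted for or stratified by entry grade.

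The cost is small. The scans do not change, and images already archived in PACS could be read with the added category. The downside is a disclosed departure from the five-grade scale as listed. Results on the original grades stay recoverable by reporting the new category separately. The category is not part of the listed classification, so the report should say that it was added. With 12 per arm or fewer, the change makes the outcome interpretable but does not make it well powered.
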